#### 4.11 Withdrawal from study

A patient may choose to end their participation in the study at any time. The patient will not be obliged to provide a reason, and the termination of participation will not influence future medical treatment nor have any other consequences for that patient, and this will be made clear to the patient when obtaining oral and written informed consent. The reason for discontinuation will be

documented (including “unknown reason”). In exceptional circumstances, the study investigator may choose to withdraw a patient from the study due to safety reasons determined by the study investigator.

The patient must have completed no less than 80% of the prescribed exercise (no less than 29 session or less than 32 minutes per session on average). This will be assessed at two weeks intervals, and subjects will be given two weeks to catch up on the missed sessions.

#### 4.12 Insurance

All patients will be covered by The Danish Patient Insurance Association for any injury that may occur as a direct consequence of study-related procedures.

#### 4.13 Practical setups

The study related procedures will be performed at the following locations:

1. Eligibility and recruitment: Department of rheumatology, Rigshospitalet and CFAS
2. Enrolment and baseline testing including VO2 max, echocardiography, muscle biopsies, and DXA: CFAS
3. PET scan: Department of Clinical Physiology, Nuclear Medicine & PET, Rigshospitalet
4. Exercise intervention: CFAS or a local collaborator with experience in exercise therapy for patients.

#### 4.15 Biobank & Data Storage

Data and associated biological material will be stored in an individual database and research biobank during the study. At the end of the study remaining biological material will be transferred to the general research biobank of CFAS. The biological material will be stored in this research biobank for a maximum of 10 years. After that, it will be destroyed. If any later studies want to make use of the biological material, this will only take place following approval by the ethical committee. Confidentiality of the subjects will be maintained by assigning subjects a study number,

keeping identifiers separate from the data and storing data in a locked file and secure computer database. Scientific reports generated from the study will not contain information that would identify the participants.

1 BACKGROUND AND RATIONAL

Systemic lupus erythematosus (SLE) is a rare chronic autoimmune disease with a varied phenotype and a predisposition for women of childbearing age¹. Systemic involvement of skin, joints and internal organs are based on a complex interaction between distinct immunopathogenic pathways including overexpression of interferons (IFN) ^{2,3}. Disease manifestations comprise flares interspaced by periods of inactive disease, cumulative accrual of organ damage and constitutive symptoms such as pain and fatigue³⁻⁷.

Patients with SLE also suffer from reduced exercise capacity with lower improvement in maximal oxygen uptake ($\dot{V}O_2\text{max}$) and fatigue severity scores (FSS) following moderate continuous exercise training (MCT) compared to healthy controls⁷⁻⁹.

High-intensity interval-training (HIIT) is a broad category of aerobic exercise programs. High intensity typically refers to exercising above a certain heart rate, ranging from 75% to 95% of the maximal heart rate (HR_{max})^{10,11}. Interval training refers to interspacing these high intensity intervals with durations ranging from 15 seconds to 5 minutes with lower intensity buffers. Multiple sets of these intervals will then compromise a total exercise duration of one session ranging from 20 to 180 minutes^{11,12}. These individual HIIT sessions are then repeated 2-5 times weekly¹⁰⁻¹².

Compared to MCT, HIIT has proven particularly effective at increasing $\dot{V}O_2\text{max}$ and alleviating fatigue in several other populations than SLE-patients, including healthy^{13,14}, middle-aged¹⁵, and elderly women^{16,17}, heart failure patients^{10,12}, as well as pre- and perioperative cancer patients^{11,18}. As of now, no randomised controlled studies have investigated the impact of HIIT on fatigue or $\dot{V}O_2\text{max}$ in SLE.

The fatigue and exercise impairment reported by patients with SLE remains unexplained but may reflect aberrations in immune function and physical adaptations to exercise¹⁹. Pathway analyses indicate a central role of IFN driven immune activation in SLE²⁰. In this respect, overexpression of type I IFNs (IFN-I) is of particular interest; often reported as a composite score reflecting whole blood mRNA expression of IFN regulated genes, denoted as the IFN gene signature (IFNGS)²¹.

Among the various effects of IFN-I is suppression of interleukin 6 (IL-6) signalling; in ex vivo studies, IFN-I has been found to attenuate IL-6 -induced phosphorylation of transducer and activator of transcription 3 (STAT3) leading to an abrogation of IL-6 activated intracellular pathways. Furthermore, IFN-I induces transcription of the suppressor of cytokine signalling 3 (SOCS3) gene further inhibiting IL-6 signaling^{22,23}.

IL-6 is a cytokine with both pro- and anti-inflammatory effects, it has multiple sources including contracting skeletal muscle²⁴. IL-6 in humans can cause lipolysis²⁵, increase glucose uptake and glycogen storage in skeletal muscle²⁶, and it may suppress production of proinflammatory cytokines such as TNF and IL-1 β ^{27,28}. Furthermore, it has been shown that IL-6 is required for exercise induced loss of visceral adipose tissue in overweight adults²⁹.

Based on these observations, this study hypothesises that in patients with SLE followed in routine care, a high IFNGS, predicts poorer improvement in aerobic capacity and fatigue following a 12- week HIIT intervention.

2 OBJECTIVES

2.1 Primary aim:

The primary aim is to investigate whether 12-week supervised HIIT has an effect on aerobic exercise capacity measured by $\dot{V}O_{2\text{max}}$ and fatigue measured by FSS in patients with SLE and if IFN-I activity determined by IFNGS negatively influences these effects.

2.2 Secondary aims:

The secondary aim is to investigate whether 12-week supervised HIIT has an effect on health related quality of life measured by SF-36³⁰ and disease activity measured by SLEDAI (with SELENA modifications)^{31,32} scores in patients with SLE and if IFN-I activity determined by IFNGS negatively influences these effects.

2.3 Other objectives:

Examine the effect of 12 weeks of HIIT on the pulmonary function of SLE patients. Considering effect modulation by IFNGS.

Examine the effects of exercise on the cardiac adaptations of SLE patients. Considering effect modulation by IFNGS.

Examine the effects of exercise on metabolic markers of SLE patients. Considering effect modulation by IFNGS.

Examine the effects of exercise on body composition in SLE patients. Considering effect modulation by IFNGS.

Examine the effect of 12 weeks of HIIT on the transcriptome related to IFN-I, IFN-II, TNF, and IL-6 in SLE patients.

3 HYPOTHESES

3.1 Primary Hypotheses

We hypothesize that 12 weeks of HIIT exercise will increase aerobic capacity and decrease fatigue score compared to no intervention, and further that the effects are modulated by IFNGS, more specifically:

1.

- a. HIIT is superior to no intervention control at improving aerobic capacity.
- b. The effect of HIIT on aerobic capacity is modulated by IFNGS, such that a higher IFNGS results in lower benefits of HIIT.

2.

- a. HIIT is superior to no intervention control at alleviating fatigue.
- b. The effect of HIIT on fatigue is modulated by IFNGS, such that a higher IFNGS results in less decrease of initial fatigue from HIIT.

Type 1 interferon induced changes to exercise adaptations in systemic lupus erythematosus patients.

Superiority is claimed if the difference is statistically significant and favors the HIIT intervention. In order to control the family-wise error rate, hypotheses 1 and 2 will be tested in parallel with Bonferroni-adjustment and hypotheses a and b will be tested hierarchically, so that hypothesis b is only tested if a is significant.

3.2 Secondary Hypotheses

Secondary hypotheses are not hierarchically tested, instead exploratory hypotheses will be controlled for false discovery rate by the Benjamini-Hochberg method³³. Secondary hypotheses are (in random order):

- HIIT is superior to no intervention control at maintaining current SLE symptoms as evaluated using SELENA-SLEDAI³⁴ by a physician.
 - This effect is modulated by IFNGS.
- HIIT is superior to no intervention control at improving health related quality of life as estimated by the SF-36 domains.
 - This effect is modulated by IFNGS.

3.3 Exploratory Hypotheses

Further exploratory hypotheses will be tested from the exploratory outcomes. There is no hierarchy of the exploratory hypotheses, instead exploratory hypotheses will be controlled for false discovery rate³³.

4 TRIAL DESIGN, DATA COLLECTION AND OUTCOMES ASSESSMENT

The study protocol, detailing the hypotheses, methods, recruitment and conduct of the study has been published in a non-peer reviewed openly accessible preprint database³⁵. In brief, the study is a randomized control trial, consisting of 2 arms, labeled exercise and control. As outlined in the publicly available protocol³⁵; initial sample size calculations were based on a t-test for changes in VO₂max. Assuming a between group difference in aerobic capacity change scores similar to the 1989 Robb-Nicholson study³⁶ (mean: 2.66, 95%CI [0.36, 4.96]); resulted in 10 completers needed in each group, if we assumed a median split of IFN-score we would require 40 completers for four groups (low IFN control, Low IFN exercise, High IFN control and high IFN exercise). We assumed as much as a 30% dropout; which required a sample size of 60 participants. After reaching 40 completers, recruitment ceased, and only further participants already enrolled for baseline examination were included, this resulted in 55 participants included in the study. These were then stratified for sex and randomly allocated 1:1 to exercise or control. At www.clinicaltrials.gov the study is identified by NCT05478018. Prior to commencement the scientific ethics committee of the capital region of Denmark approved to trial with identifier H-21039032. The trial primarily took place at Centre for Physical Activity on Rigshospitalet, [name]. Recruitment took place primarily at the center for vasculitis and spine diseases on Rigshospitalet in [name]. 82-Rb-Pet-CT scans were conducted at the department of clinical physiology at Rigshospitalet, [name].

[figure not shown]

Figure 1 - Graphical hypothesis

The exercise group underwent 12 weeks of thrice weekly 45 minute HIIT exercise sessions, with 4 intervals of 4 minutes of high intensity exercise, defined as a heart rate above 85% of the maximal heart rate interspersed with 3 minute active breaks of pedaling against light resistance (less than 20% wattmax).

As noted above the hypotheses were that these 12 weeks would improve aerobic capacity and fatigue in SLE patients, and that it would improve more in patients with lower IFNGS.

Participants flow through the project with a screening visit, where aerobic capacity is assessed, a baseline visit with most of the outcomes, and a baseline-acute bout session consisting of one exercise bout and the measurements of the autonomic nerve system. A subgroup of patients will then undergo a 82-Rb-rest-stress-PET-CT evaluating cardiac adaptation. Patients are then randomized to exercise or control. Whereafter they will undergo a followup visit, another acute bout (termed the follow-up acute bout) and at last if they did one at baseline, they will do a repeat 82-Rb-rest-stress-PET-CT.

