### **3.9.18 Data analysis**

At least 10 participants in each intervention group and 10 participants in each control group, will be included to obtain a significance level of 0.05 with a power of 80% to observe an increase in VO2max of 1.14ml/kg/min with a SD of 2.15 in the control group and an increase in VO2max of 3.80ml/kg/min with a SD of 3.34 in the intervention group based on a previous publication. If we assume a drop-out rate of less than 30% with 15 participants in each group, we will have at least a power of 80% even with 30% drop-out. With 14 participants in each group, we will achieve a power of 90%.

Similar results were gained when examining the study by Boström et al. were the control group had an increase in VO2max of 1.7ml/kg/min with an SD of 1.3 and the intervention group had an increase of 3.2ml/kg/min with an SD of 1.2. A significance of 0.05 and a power of 80% requires 12 subjects in each group.

Since we hope to be able to part our groups into patients with higher IFNGS being the patients with M3.4 and M5.12 and we assume one third of our patients will be in this group, including 30 patients for intervention will give us 10 “high IFNGS intervention” patients in total for this power calculation.

Results will be analysed according to a pre-defined statistical analysis plan and initial modelling of the primary outcome will be based on Analysis of Covariance (ANCOVA) performed with change (post-measure minus pre-measure) as the dependent outcome, with a fixed factor for group (two levels) and applying the value at baseline as a covariate.

$$k = \frac{n_2}{n_1} = 1$$

$$n_1 = \frac{(\sigma_1^2 + \sigma_2^2/K)(z_{1-\alpha/2} + z_{1-\beta})^2}{\Delta^2}$$

$$n_1 = \frac{(2.15^2 + 2.15^2/1)(1.96 + 0.84)^2}{2.66^2}$$

$$n_1 = 10$$

$$n_2 = K * n_1 = 10$$

$\Delta = |\mu_2 - \mu_1|$  = absolute difference between two means  
 $\sigma_1, \sigma_2$  = variance of mean #1 and #2  
 $n_1$  = sample size for group #1  
 $n_2$  = sample size for group #2  
 $\alpha$  = probability of type I error (usually 0.05)  
 $\beta$  = probability of type II error (usually 0.2)  
 $z$  = critical Z value for a given  $\alpha$  or  $\beta$   
 $k$  = ratio of sample size for group #2 to group #1

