6.2 Multiple testing and significance

Multiple testing of the co-primary endpoints will be handled by Bonferroni-adjustment (i.e. by multiplying p-values by two and presenting estimated treatment effects with 97.5% confidence intervals). Tests of treatment effect and effect modification by IFNGS will be carried out sequentially, so that effect modification will only be tested if a significant treatment effect is found. This is in accordance with the alpha set at p=0.05 in the original protocol without Bonferroni correction. The p-values from the secondary and exploratory analyses will be adjusted for multiple testing using the method of Benjamini and Hochberg³³, which control the false discovery rate (FDR). Adjustment will be carried out for secondary and exploratory end points separately and for tests of treatment effect and effect modification separately. In all analyses an adjusted p-value < 0.05 will be considered statistically significant.

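### The SAP's 10 completers per cell was sized at two-sided 0.05, but VO2max is tested at 0.025; the size and power were not restated, and the cell-level figure drops to 70% (63% by t-test)

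*SAP*

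**What the plan says.** Protocol 3.9.18 sizes the trial on the change in VO2max. At least 10 participants per group are planned "to obtain a significance level of 0.05 with a power of 80" percent. The inputs in the text are a change of "1.14ml/kg/min with a SD of 2.15 in the control group" and "3.80ml/kg/min with a SD of 3.34 in the intervention group". The printed formula uses z values of 1.96 and 0.84 and enters 2.15 as the SD of both groups.

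SAP section 4 describes this as a t-test calculation on a between-group difference ("mean: 2.66, 95%CI [0.36, 4.96") and states that it "resulted in 10 completers needed in each group". With a median split of the IFN score, "we would require 40 completers for four groups": low and high IFN in each arm. Allowing for 30% dropout gave a target of 60. Recruitment ceased at 40 completers; participants already enrolled for baseline examination were kept, giving 55.

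SAP 3.1 tests the VO2max and FSS hypotheses in parallel with Bonferroni adjustment, and tests the IFNGS hypothesis for an endpoint only after its treatment effect is significant. SAP 6.2 implements this with doubled p-values and 97.5% confidence intervals. It adds: "This is in accordance with the alpha set at p=0.05 in the original protocol without Bonferroni correction".

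**The concern.** The 10 per cell and the level at which VO2max is tested come from different decision rules. The SAP introduces the Bonferroni split and carries the protocol's number forward without recalculating it. SAP section 4 is the SAP's only sample-size justification, and it explains why recruitment stopped at 40 completers. A reader who takes it together with the SAP 6.2 sentence on alpha would conclude that the protocol's 80% still applies under the SAP's own rule. At the level of the cells for which it was computed, it does not.

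**Working it through.** **Inputs.** Difference 2.66 ml/kg/min (3.80 − 1.14, Protocol 3.9.18; repeated in SAP 4). SD 2.15 in both groups, as entered in the protocol's formula. Two-sided alpha 0.05 in the protocol; 0.05/2 = 0.025 for VO2max in SAP 6.2. Power 80%. 10 completers per cell, hence 20 per arm.

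**1. Reproduce the plan's figure.** n = 2 × SD² × (z₁₋α/₂ + z₁₋β)² / Δ²

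- With the protocol's rounded z values: 2 × 2.15² × (1.96 + 0.84)² / 2.66² = 9.245 × 7.84 / 7.0756 = 10.24.
- The protocol rounds this down to 10. With unrounded z values it is 10.26.

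**2. Repeat at 0.025.** z₁₋α/₂ becomes 2.2414, so the squared sum is (2.2414 + 0.8416)² = 9.505.

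- n = 9.245 × 9.505 / 7.0756 = 12.42, so 13 per cell.
- By t-test, the test SAP 4 names, 13 gives 77.2% and 14 gives 80.8%, so 14 are needed.
- Under the normal formula the ratio 9.505 / 7.849 = 1.21 is free of effect and SD: the change of level alone raises the required n by about 21%.

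**3. Power with 10 per cell.** SE = 2.15 × √(2/10) = 0.9615, and 2.66 / 0.9615 = 2.767.

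| Two-sided alpha | Normal approximation | t-test |
|---|---|---|
| 0.05 | Φ(2.767 − 1.960) = 79.0% | 74.4% |
| 0.025 | Φ(2.767 − 2.241) = 70.0% | 63.0% |

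**4. The protocol's second source.** The difference is 3.2 − 1.7 = 1.5, with SDs 1.3 and 1.2.

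- The required n goes from 10.9 at 0.05 to 13.2 at 0.025. The protocol states 12 per group at 0.05.
- With 10 per group at 0.025, power is 67.0% (normal) or 59.9% (t).

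**5. The VO2max treatment test that is planned.** Hypothesis 1a compares whole arms. At 20 completers per arm and alpha 0.025:

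| SDs (control, exercise) | Normal | t-test |
|---|---|---|
| 2.15, 2.15 (entered in the formula) | 95.3% | 93.8% |
| 2.15, 3.34 (stated in the protocol text) | 77.4% | 73.8% (Welch) |

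For the first row, SE = 2.15 × √(2/20) = 0.680, 2.66 / 0.680 = 3.912, and Φ(3.912 − 2.241) = 95.3%. If all 55 participants contributed, about 27 per arm, the rows become 98.9% / 98.6% and 89.2% / 87.3%.

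**6. The IFNGS test.** SAP 6.1 tests IFNGS on a continuous scale through an interaction, and the documents give no effect size for it. As an illustration only, assume a median-split difference-in-differences of 2.66, SD 2.15 and 10 per cell. Then SE = √(4 × 2.15² / 10) = 1.360 and power at 0.025 is Φ(2.66 / 1.360 − 2.241) = 39%. The two-group 70% is therefore not a stand-in for the power of the interaction.

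**The case against.** The strongest reply is that no planned test has 10 against 10. In SAP 4 the 10 is one of four cells. Hypothesis 1a is tested on whole arms in the modified intention-to-treat set, and IFNGS enters as a continuous modifier. The tertile columns of the planned Table 3 are descriptive, beside an interaction estimate. This stands, and it sets the limit of the point.

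A reader might infer from the 70% or 63% that the primary tests are underpowered. The documents do not support that. For VO2max, the whole-arm test keeps about 94–95% on the inputs the plan entered. It falls below 80% at 20 per arm only with the protocol's stated exercise-arm SD of 3.34, which is a separate matter from alpha. For FSS, the documents give no effect or SD, so nothing can be said about its power. Nor can the concern be that a null result within IFN cells would be misread, because no inference within cells is planned.

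It is also fair to say that 63% should not be set against a nominal 80%. The t-test figure was already 74.4% at 0.05, so alpha alone costs 9 points (normal) or 11 points (t).

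Two further replies carry some weight. SAP 4 calls the calculation initial and does not itself repeat the 80%. And the SAP 6.2 sentence can be read coherently: doubled p-values judged against 0.05 hold the family-wise level at the protocol's 0.05. That reading is right about the family, but it leaves unsaid that VO2max now faces a stricter level than the one behind the 10. Finally, 10 per cell is close to a floor, since 55 were included and the mixed model keeps incomplete participants. That helps the power achieved, but does not correct the stated rationale.

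**Conclusion.** The inconsistency is real but limited. The SAP relies on a cell size computed at two-sided 0.05 while testing VO2max at 0.025, and does not say so. On the protocol's entered inputs, 10 per cell gives 70% (63% by t-test) instead of 79% (74%), and 80% needs 13 (14 by t-test). The percentages rest on the 2.66 difference and an SD of 2.15 in both arms. The direction does not depend on them; the percentages do, and with SDs of 2.15 and 3.34 the power with 10 per cell at 0.025 is 45% (normal).

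What is affected is the sizing argument behind the four-cell design and the recruitment stop, for VO2max only. It is a fault in the stated justification, not evidence that the VO2max treatment test or the FSS test lacks power.

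**What to change.** - **SAP section 4:** state that 10 completers per cell was computed at two-sided 0.05, and that at the 0.025 used for VO2max it gives 70% (63% by t-test), with 13 (14 by t-test) needed for 80%.
- **Same section:** give the whole-arm VO2max power at 0.025 as the power of the primary VO2max test, with the SDs assumed: 95% (94% by t-test) at 20 per arm with SD 2.15 in both arms, and about 77% (74%) with SDs of 2.15 and 3.34. State that two-group power at 10 per cell is not the power of the continuous IFNGS interaction.
- **SAP 6.2:** reword the sentence on alpha to say that the family-wise level stays at 0.05 while each co-primary endpoint is tested at 0.025, which is stricter than the level used for the sample size.

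The cost is a few sentences. No test, recruitment or trial procedure changes; the only downside is that the stated power looks less favourable.

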6.1 Statistical Methods

Evaluation of the treatment effect in the primary analyses will be performed using a constrained linear mixed effect model including sex, follow-up time (categorical), treatment, and the constrained treatment*time interaction as fixed effects, and with an unstructured covariance pattern to account for repeated measurements on each study participant; as a sensitivity analysis, the interaction between sex*time will also be considered, but not included in the main model, as there seem to be no interaction for this in exercisers without SLE at 12 weeks⁴⁴. Effect modification by IFNGS will be evaluated by further including IFNGS (continuous scale), the IFNGS- -time interaction, and the constrained treatment*time*IFNGS interaction in the linear mixed model. Missing data will be handled implicitly by maximum likelihood estimation in the linear mixed model.

For the exploratory outcomes in the oral glucose tolerance test and acute exercise bout domains blood was sampled 6 or 9 times (respectively) throughout the measurements, a linear mixed effect model will be used on summary scores (such as DI or Matsuda Index).

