12.1 Tables in paper

Table 1. Baseline characteristics separated by randomization group. Aerobic capacity, weight & waist circumference separated by screening/baseline.

Table 2. Changes from baseline and estimated treatment differences for the Primary and secondary outcomes, and related exploratory outcomes as suggested by the CONSORT statement.

Table 3. As table 2 but with randomization groups further divided according to percentiles of the IFN-score at baseline and the estimated treatment difference replaced by the estimate for de IFN-score*randomization group interaction.

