16 UNFORMATTED TABLES WITH INTENDED CONTENT

Table 1 Baseline characteristics

	Control	Exercise	Total
Age (years)			
Sex (N (%)) female)			
SLE duration (years)			
SLE activity markers			
SLEDAI			
SLICC			
B2MG			
LYMPHOCYTES			
THROMBOCYTES			
Antibodies			
Anti-Sm			
ANTI-DsDNA			
NEITHER ANTI-DsDNA or ANTI-sm			

Table 2 – Change scores without IFN-difference

Outcome	Change from 0 to 12 weeks Mean \pm SD		Estimated treatment difference (95% CI, p-Value)
	Control (n=xx)	Exercise (n=yy)	
VO2max			
FSS			
SF-36 Aggregate Physical Component			
SF-36 Aggregate Mental Component			
Etc.			

Table 3 – Change scores with IFN quantiles							
Outcome	Change from 0 to 12 weeks Mean \pm SD						Estimated IFN:Treatment interaction (95% CI, p-Value)
	Control (n=xx)			Exercise (n=yy)			
	IFN-low	IFN-Mid	IFN-High	IFN-Low	IFN-Mid	IFN-High	
VO2max							
FSS							
SF-36 Aggregate Physical Component							
SF-36 Aggregate Mental Component							
Etc.							

IFN-Low = Lower 33% percentile of the IFN-scores, IFN-Mid 33%-66% percentile of the IFN-scores, IFN-High 67%-100% of IFN-scores.

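### Table 2 of the SAP prints 95% intervals where section 6.2 requires 97.5%; the protocol's 10 high-IFNGS exercisers become about 7 after drop-out; and 10 per cell does not give the stated 80% power

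*SAP*

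**What the plan says.** **Interval level.** SAP 3.1 tests hypotheses 1 (VO2max) and 2 (FSS) in parallel with Bonferroni adjustment. Within each, the order is hierarchical, "so that hypothesis b is only tested if a is significant". SAP 6.2 implements this by doubling the p-values and "presenting estimated treatment effects with 97.5% confidence intervals". In SAP 16, however, the last column of Table 2 is headed "Estimated treatment difference (95% CI, p-Value" and that of Table 3 "Estimated IFN:Treatment interaction (95% CI, p-Value". Both shells contain VO2max and FSS rows, together with SF-36 and further rows. SAP 12.1 describes Table 3 as Table 2 split by IFN percentiles, with "the estimated treatment difference replaced by the estimate for de IFN-score*randomization group interaction".

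**Sample size.** SAP 4 bases the size on a t-test for VO2max change with 10 completers per group, and then: "if we assumed a median split of IFN-score we would require 40 completers for four groups". It allows 30% drop-out, which gives 60. It reports that recruitment stopped after 40 completers and that 55 were included. Protocol 3.9.18 gives the inputs: change 1.14 (SD 2.15) in controls and 3.80 (SD 3.34) with exercise, alpha 0.05, power 80%. Its worked formula enters 2.15 for both arms. The same section takes one third of 30 exercisers as 10 high-IFNGS patients for the power calculation, and elsewhere allows drop-out of less than 30%.

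**Analysis of IFNGS.** SAP 6.1 keeps IFNGS continuous and tests "the constrained treatment*time*IFNGS interaction in the linear mixed model". Table 3 displays thirds: "IFN-Low = Lower 33% percentile of the IFN-scores".

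**The concern.** IFNGS modification is the protocol's primary aim and half of the SAP's primary hypotheses, so the numbers tied to IFN subgroups will be read as support for it. Two of them do not carry the power attached to them. The protocol's high-IFNGS count is taken before drop-out. The 10 per cell reaches 80% only approximately, and only if the exercise-arm SD is replaced by the smaller control SD.

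Separately, the table that will report the co-primary results does not follow the SAP's own multiplicity rule. With doubled p-values beside 95% intervals, the two can disagree for the same row. That happens for any unadjusted p between 0.025 and 0.05: the adjusted p is not significant, but the interval excludes zero.

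**Working it through.** **1. Interval level.** Take an unadjusted p of 0.03. Adjusted p = 2 x 0.03 = 0.06, not significant. The 95% interval excludes zero because 0.03 < 0.05. The 97.5% interval includes zero because 0.03 > 0.025, so it agrees with the adjusted p. The width ratio is t(0.9875)/t(0.975) = 1.15 at 36 to 53 degrees of freedom.

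**2. The plan's own figures** (difference 3.80 - 1.14 = 2.66)
- Protocol formula as entered: (2.15² + 2.15²)(1.96 + 0.84)²/2.66² = 9.245 x 7.84/7.0756 = 10.24, printed as 10.
- Four cells: 4 x 10 = 40. Drop-out: 40/0.7 = 57.1, so 58, consistent with the SAP's 60. Conversely 60 x 0.7 = 42, or 10.5 per cell.
- Same formula with both stated SDs: (4.6225 + 11.1556) x 7.84/7.0756 = 17.48, so 18 per group.

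**3. High-IFNGS exercisers in the protocol**
- Before drop-out: 30 x 1/3 = 10.
- At 30% drop-out: 10 x 0.7 = 7.
- Exercisers needed to keep 10 completers: 10/(0.7 x 1/3) = 42.9, so about 43.

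**4. Power of exercise v control within a stratum.** Two-sided t-test (noncentral t), difference 2.66, alpha 0.05. For unequal SDs the root mean square is used: sqrt((2.15² + 3.34²)/2) = 2.81.

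| Completers | SD 2.15 in both arms | SDs 2.15 and 3.34 |
|---|---|---|
| 10 v 10 | 74% | 52% |
| 7 v 7 | 57% | 37% |

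At 10 v 10 and SD 2.15 the normal approximation gives 79%, which is why the formula appears to deliver 80%. The t-test needs 12 per group.

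**5. What the 40 does not size.** Four cells of 10 address exercise v control inside each IFN half. The test of 1b is a difference in slope on continuous IFNGS. Neither document states such a slope, and neither sizes FSS. For orientation only, assume change scores, alpha 0.025, IFNGS in SD units, equal arms, and the stated SDs taken as residual. Then SE = sqrt((s0² + s1²)/(N/2)) with N - 4 degrees of freedom, and the slope detectable with 80% power, in ml/kg/min per SD of IFNGS, is:

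| N analysed | SD 2.15 in both arms | SDs 2.15 and 3.34 |
|---|---|---|
| 40 | 2.17 | 2.84 |
| 55 | 1.83 | 2.39 |

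**The case against.** SAP 4 is open about where the 40 comes from: a VO2max t-test and four groups. Neither document claims power for 1b or 2b. Recruitment is over, the model treats IFNGS as continuous, and no planned analysis uses the protocol's one-third group. The protocol's wording on the split is tentative, and its 30% is an upper bound attached to 15 per group. The table shells are labelled unformatted, and 6.2 is the governing text. All of this stands, and it limits the point to correcting statements and one table level.

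Four stronger readings are tempting and are not supported.
- A reader might infer that the SAP's target ignores drop-out. It does not: 60 x 0.7 = 42 completers.
- A reader might infer that the trial has been shown to be underpowered for the interaction. With no slope in the documents, the detectable slopes above are conditional figures. The planned constrained model should do somewhat better than change scores, by an amount that depends on correlations the documents do not give.
- A reader might infer that Table 3 breaches 6.2 outright. That section names treatment effects only. The 97.5% level for the interaction follows from the Bonferroni rule in 3.1, which covers hypotheses 1 and 2 including their b parts.
- A reader might take one third against a median split as a plain error. The SAP cites a preprint protocol that is not among the documents supplied, so this may be a version difference.

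Nor does the point undermine 1a as a whole. With 20 per arm at alpha 0.025, the same t-test has about 94% power (SD 2.15) or 74% (SDs 2.15 and 3.34).

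**Conclusion.** The point holds in three limited parts.

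1. Table 2 contradicts SAP 6.2 for the VO2max and FSS rows. This needs no assumption. Table 3 should follow for consistency.
2. The protocol's 10 high-IFNGS exercisers become about 7 at the drop-out limit stated in the same section. Power within that stratum is then 57% or 37%, depending on which of the protocol's SDs apply and assuming 7 comparable controls and a difference of 2.66. The split also differs between the two documents.
3. Ten per cell gives 74% or 52% power rather than 80%, and the 40 was not derived for 1b, 2b or FSS. The lack of a power statement for the interaction is missing detail, not a false claim.

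All of this is best settled before analysis starts, since SAP 8 has the plan published before then.

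**What to change.** - **Tables.** Use 97.5% intervals for the VO2max and FSS rows of Table 2, and for the same two rows of Table 3. Leave the other rows as they are.
- **SAP note on protocol 3.9.18.** Restate the high-IFNGS exercise count as about 7 after 30% drop-out, reconcile the one-third share with the median split, and report the actual counts.
- **SAP section 4.** If the 40 is kept as four cells of 10, say that it is not a power claim for 1b, 2b or FSS. Say also that 10 per cell gives about 74% power with SD 2.15 in both arms or 52% with the stated SDs, and that the protocol formula with both stated SDs gives about 18 per group.
- **Optional.** Give the IFNGS slope detectable at the achieved n with its assumptions declared: about 1.8 to 2.8 ml/kg/min per SD of IFNGS under those in the working.

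The cost is a short note and an interval level in two shells. The primary-outcome intervals become about 15% wider and the stated power less favourable. Enrolment and the model do not change.
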